2.8.5 Other safety data

[REDACTED]

2.8.5.2 ECG

Number and percentage of patients with notable abnormal ECG result will be summarized for entire treatment period. Summary statistics will be presented for ECG variables by visit and treatment group.

A listing of all newly occurring or worsening abnormalities will be provided.

Notable abnormal is defined as:

- QTcF > 450 msec
- QTcF > 480 msec
- QTcF > 500 msec
- QTcF changes from baseline > 30 msec
- QTcF changes from baseline > 60 msec
- PR > 250 msec

2.8.5.3 Vital signs

Analysis in vital sign measurement using descriptive summary statistics for the change from baseline for each post-baseline visit will be performed by vital sign and treatment group. Change from baseline will only be summarized for subjects with both baseline and post-baseline values and will be calculated as:

[figure not shown]
$$\text{change from baseline} = \text{post-baseline value} - \text{baseline value}$$

[figure not shown]
[figure not shown]
[figure not shown]
Only “on-treatment” vital signs will be summarized (i.e. assessments within last dose plus 84 days). All vital signs will be listed with “on-treatment” flag displayed.

[figure not shown]
The number and percentage of subjects with newly occurring notable vital signs will be presented. Criteria for notable vital sign abnormalities are provided in [Table 2-9](#) below. A listing of subjects with newly occurring notably abnormal vital signs will be provided.

Table 2-9 Criteria for notable vital sign abnormalities

Vital sign (unit)	Notable abnormalities
Systolic blood pressure (mmHg)	>= 140 mmHg or < 90 mmHg
Diastolic blood pressure (mmHg)	>=90 mmHg or <60 mmHg
Pulse (bpm)	> 100 bpm or <60 bpm

2.14 Interim analysis

A Week 16 primary efficacy analysis will be conducted when the last patient complete his Week 16 visit. All the safety data up to this date will be summarized. Efficacy data up to Week 16 visit for each patients will be summarized. All data up to this date will be listed.

3 Sample size calculation

The sample size has been calculated to detect a clinical relevant treatment difference (i.e. 15%) between secukinumab 300 mg every two weeks and secukinumab 300 mg every four weeks. Based on this, the total sample size is approximately 330 subjects, with body weight ≥ 90 kg at randomization. i.e., 165 subjects will be randomized to each dose regimen (300 mg every 2 weeks and 300 mg every 4 weeks) using a balanced randomization.

Secukinumab 300 mg every two weeks will be tested versus secukinumab 300 mg every four weeks with respect to the primary endpoint PASI 90 response at Week 16, and sequentially the secondary endpoint IGA mod 2011 0 or 1 at Week 16. The family-wise type-I-error will be 2.5% (one-sided)

4 Change to protocol specified analyses

5 Appendix

5.1 Imputation rules

5.1.1 Study drug

Any partial dates will be imputed as follows:

We take the earlier day of

- The last day in the month and
- The end day of the corresponding epoch

5.1.2 AE date imputation

Impute AE end date:

1. If the AE end date 'month' is missing, the imputed end date should be set to the earliest of the (min (last visit date, last dose date + 84 days), 31DECYYYY, date of death).
2. If the AE end date 'day' is missing, the imputed end date should be set to the earliest of the (min (last visit date, last dose date + 84 days), last day of the month, date of death).
3. If AE 'year' is missing or AE is ongoing, the end date will not be imputed.

Impute AE start date:

Before imputing AE start date, find the AE start reference date.

1. If the (imputed) AE end date is complete and the (imputed) AE end date < treatment start date then AE start reference date = min(informed consent date, earliest visit date).
2. Else AE start reference date = treatment start date
 1. If the AE start date 'year' value is missing, the date uncertainty is too high to impute a rational date. Therefore, if the AE year value is missing, the imputed AE start date is set to NULL.
 2. If the AE start date 'year' value is less than the treatment start date year value, the AE started before treatment. Therefore:
 - a. If AE 'month' is missing, the imputed AE start date is set to the mid-year point (01JulYYYY).
 - b. Else if AE 'month' is not missing, the imputed AE start date is set to the mid-month point (15MONYYYY).
 3. If the AE start date year value is greater than the treatment start date year value, the AE started after treatment. Therefore:
 - a. If the AE month is missing, the imputed AE start date is set to the year start point (01JanYYYY).
 - b. Else if the AE month is not missing, the imputed AE start date is set to the later of (month start point (01MONYYYY), AE start reference date + 1 day).
 4. If the AE start date year value is equal to the treatment start date year value:
 - a. And the AE month is missing the imputed AE start date is set to the AE reference start date + 1 day.
 - b. Else if the AE month is less than the treatment start month, the imputed AE start date is set to the mid-month point (15MONYYYY).
 - c. Else if the AE month is equal to the treatment start date month or greater than the treatment start date month, the imputed AE start date is set to the later of (month start point (01MONYYYY), AE start reference date + 1 day).

If complete (imputed) AE end date is available and the imputed AE start date is greater than the (imputed) AE end date, then imputed AE start date should be set to the (imputed) AE end date.

5.1.3 Concomitant medication date imputation

Impute CM end date:

1. If CM end day is missing and CM month/year are non-missing then impute CM day as the minimum of treatment end date and the last day of the month.
2. If CM end day/month are missing and CM year is non-missing then impute CM day as the minimum of treatment end date and the end of the year (31DECYYYY).
3. If imputed CM end date is less than the CM start date, use the CM start date as the imputed CM end date.

Impute CM start date:

1. If the CM start date year value is missing, the imputed CM start date is set to one day prior to treatment start date.
2. If the CM start date year value is less than the treatment start date year value, the CM started before treatment. Therefore:

- a. If the CM month is missing, the imputed CM start date is set to the mid-year point (01JulYYYY).
 - b. Else if the CM month is not missing, the imputed CM start date is set to the mid-month point (15MONYYYY).
 3. If the CM start date year value is greater than the treatment start date year value, the CM started after treatment. Therefore:
 - a. If the CM month is missing, the imputed CM start date is set to the year start point (01JanYYYY).
 - b. Else if the CM month is not missing, the imputed CM start date is set to the month start point (01MONYYYY).
 4. If the CM start date year value is equal to the treatment start date year value:
 - a. And the CM month is missing or the CM month is equal to the treatment start date month, then the imputed CM start date is set to one day prior treatment start date.
 - b. Else if the CM month is less than the treatment start date month, the imputed CM start date is set to the mid-month point (15MONYYYY).
 - c. Else if the CM month is greater than the treatment start date month, the imputed CM start date is set to the month start point (01MONYYYY).
- If complete (imputed) CM end date is available and the imputed CM start date is greater than the (imputed) CM end date, then imputed CM start date should be set to the (imputed) CM end date.

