## 4.2 Exclusion criteria

Subjects fulfilling any of the following criteria are not eligible for inclusion in this study. No additional exclusions may be applied by the investigator, in order to ensure that the study population will be representative of all eligible subjects.

1. Use of other investigational drugs at the time of enrollment, or within 5 half-lives of enrollment, or within 4 weeks until the expected pharmacodynamic effect has returned to baseline, whichever is longer; or longer if required by local regulations.
2. History of hypersensitivity to any of the study drug constituents.
3. Forms of psoriasis other than chronic plaque-type (e.g., pustular, erythrodermic and guttate psoriasis) at screening or Randomization.
4. Drug-induced psoriasis (i.e., new onset or current exacerbation from beta-blockers, calcium channel inhibitors or lithium) at Randomization.
5. Ongoing use of prohibited treatments. Washout periods detailed in the protocol have to be adhered to (Table 5-1). Subjects not willing to limit UV light exposure (e.g., sunbathing and / or the use of tanning devices) during the course of the study will be considered not eligible for this study since UV light exposure is prohibited.

Note: administration of live vaccines 6 weeks prior to Randomization or during the study period is also prohibited.

6. Previous exposure to secukinumab (AIN457) or any other biologic drug directly targeting IL-17 or the IL-17 receptor.
7. Pregnant or nursing (lactating) women
8. Women of child-bearing potential (WoCBP), defined as all women physiologically capable of becoming pregnant, unless they are using basic methods of contraception during the entire study or longer if required by locally approved prescribing information (e.g. in EU 20 weeks).

Basic contraception methods include:

- Total abstinence (when this is in line with the preferred and usual lifestyle of the subject. Periodic abstinence (e.g., calendar, ovulation, symptothermal, post-ovulation methods) and withdrawal are not acceptable methods of contraception.
- Female sterilization (have had surgical bilateral oophorectomy [with or without hysterectomy], total hysterectomy or tubal ligation at least six weeks before taking study treatment). In case of oophorectomy alone, only when the reproductive status of the woman has been confirmed by follow-up hormone level assessment.

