2.4.4 Prior, concomitant and post therapies

Medications will be identified using Novartis Drug and Therapy Dictionary (NovDTD) including Anatomical Therapeutic Chemical (ATC) code. Prior and concomitant treatments will be summarized by treatment group for the safety set unless otherwise specified. Concomitant treatments will be displayed for the treatment period.

Prior and concomitant medications will be summarized by treatment group in separate tables. Medications will be presented in alphabetical order, by ATC codes and grouped by *anatomical main group* (the 1st level of the ATC codes). Tables will also show the overall number and percentage of subjects receiving at least one drug of a particular ATC code and at least one drug in a particular anatomical main group.

Prior medications are defined as drugs taken and stopped prior to the first dose of study treatment. Any medication given at least once between the day of first dose of randomized study treatment, and last dose plus 84 days or last study visit (including follow-up visits) whichever occurs earlier will be a **concomitant** medication, including those which were started pre-baseline and continued into the treatment period.

Psoriasis specific summaries of prior and/or concomitant medication will be presented as in [Table 2-3](#), but as well for topical, phototherapy and photochemotherapy (yes/no) using the randomized set.

In addition, medical procedures and significant non-drug therapies as coded in MedDRA will be summarized.

Prior or concomitant medication will be identified based on recorded or imputed start and end dates of medication taken. Further rules will be given in [Section 5](#).

Table 2-3 Summary of previous psoriasis therapy

Level 1 description	Level 1 outcome	Level 2 description	Level 2 outcome	
previous therapy	yes/no			
systemic	No			
	Yes	number	1	
			2	
			>=3	
		failure*	no	
yes				
biologic	No			
	Yes	failure*	no	
			yes	
		type of previous biologic		
		anti-p40	no	
			yes	
		anti-TNF	no	
yes				
non-biologic systemic	No			
	Yes	failure*	no	
			yes	
		failure* to at least 2	no	
yes				

*: at least one therapy with lack of primary efficacy or lack of secondary efficacy or lack of tolerability

[figure not shown]

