5.1.3.1 Prior therapies date imputation

See [Section 5.1.3](#).

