5.1.3.2 Post therapies date imputation

See [Section 5.1.3](#).

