5.4.1.2 Multiple imputations for response variables

Primary and secondary endpoints will be evaluated by Logistic regression and odds ratio estimate as described in the primary analysis method with multiple imputations for missing values. In addition, logistic regression analysis for [REDACTED], PASI 90, [REDACTED] and IGA mod 2011 0 or 1 response by visits will be analyzed using multiple imputation method.

In the multiple imputations analysis the response status will be imputed based on the individual treatment arm information.

Multiple imputation (MI) is a simulation based approach where missing values are replaced by multiple Bayesian draws from the conditional distribution of missing data given the observed data and covariates, creating multiple completed data sets. These completed data sets can then be analyzed using standard methods. [Rubin \(1987\)](#) presented rules how to combine the multiple sets of estimates to produce overall estimates and confidence intervals that adequately incorporate missing data uncertainty.

Missing values for the 'change from baseline PASI score' and 'IGA mod 2011 score' will be imputed simultaneously based on an underlying joint normal distribution and using a Markov Chain Monte Carlo (MCMC) method. The change from baseline in PASI score appears to follow closer to a normal distribution than the actual PASI score. Assuming normality for the 'IGA mod 2011 score' is motivated by [Schaefer \(1997\)](#), where it was shown that the multivariate normal approximation for the imputation of incomplete categorical and binary data is robust.

The imputations will be done separately for each treatment group including baseline weight, failure to at least one previous biologic (yes/no), and number of previous systemic therapies as additional covariates.

Summary statistics for [REDACTED], PASI 90, [REDACTED] and IGA mod 2011 0 or 1 response by visit will be presented in contingency tables with multiple imputations method.

The number of imputations will be set to 100, the seed for the random function will be set to 4572326 for this study. To generate the multiple imputed data sets, the SAS procedure MI can be used as follows:

The input data set <pasi_iga> should have one record per subject with baseline PASI score and IGA mod 2011 score as well as all changes from baseline PASI and post-baseline IGA mod 2011 score.

ODS LISTING CLOSE;

```
ODS OUTPUT MissPattern=msgpat VarianceInfo=varinfo ParameterEstimates=param;

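### A previous therapy with a year-only stop date in the calendar year of first dose is imputed as ending on study and tabulated as concomitant instead of prior

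*SAP*

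**What the plan says.** SAP 5.1.3.1, headed "Prior therapies date imputation", consists only of a pointer to 5.1.3, the section on concomitant-medication dates. In 5.1.3, a stop date with year but no month is handled by the instruction to "impute CM day as the minimum of treatment end date and the end of the year (31DECYYYY". If month and year are known, the last day of that month is used, again no later than treatment end. Neither rule refers to first dose.

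SAP 2.4.4 counts a drug as prior only if it was stopped before first dose. A drug given at least once from first dose up to the earlier of last dose plus 84 days and the last visit is concomitant. It adds: "Prior or concomitant medication will be identified based on recorded or imputed start and end dates of medication taken".

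Protocol 4.2, exclusion 5, states: "Washout periods detailed in the protocol have to be adhered to". Protocol Table 5-1 sets the washouts before randomization: 24 weeks for alefacept, briakinumab, efalizumab and ustekinumab; 12 weeks for other biologics; 4 weeks for other systemic treatments; 2 weeks for phototherapy and topicals.

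**The concern.** An end-date rule that leans late is reasonable for drugs in use during the trial. Applied to therapy history it overrides something already known: the drug had been stopped before the subject entered. History records are also where a bare year is a plausible entry. The concomitant tables would then show biologics or systemics on study that were not taken on study, and the prior-medication tables would lose them. A reader of the study report could take such entries for confounding treatment or protocol violations.

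The SAP guards against this kind of error elsewhere. The diagnosis-date rule (5.1.3.3) has a branch for a year equal to the consent year. The adverse-event rule (5.1.2) uses a different reference date for events that ended before treatment. The end date of a prior therapy has no such guard.

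**Working it through.** The plan states no figure on this point, so there is none to reproduce. The check applies the rules as written.

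**Step 1. When is a record affected?** For a year-only stop, imputed end = min(treatment end, 31 December of the recorded year).
- Recorded year before the year of first dose: the result is no later than 31 December of that earlier year, which precedes first dose. The record stays prior.
- Recorded year equal to the year of first dose: treatment end and 31 December are both on or after first dose, so their minimum is too. The record becomes concomitant.

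So a washed-out year-only record is misclassified if and only if stop year = first-dose year.

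**Step 2. Worked case.** First dose 16 September 2019, treatment end taken as 48 weeks later (17 August 2020), therapy with year-only dates:

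| Recorded year | Imputed start | Imputed end | Class |
|---|---|---|---|
| 2017 | 1 Jul 2017 | 31 Dec 2017 | prior |
| 2018 | 1 Jul 2018 | 31 Dec 2018 | prior |
| 2019 | 15 Sep 2019 | 31 Dec 2019 | concomitant |

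Methotrexate with its 4-week washout must have stopped by 19 August 2019, yet the last row ends it 106 days after first dose. Stopping treatment early does not help: with treatment end on 1 November 2019 the imputed end is 1 November 2019. The start-date defaults are not at fault. Over 1,084,780 combinations of first dose and true earlier start, none was imputed on or after first dose.

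**Step 3. Month recorded.** Misclassification now needs stop and first dose in the same calendar month. Gaps of 84 or 168 days rule that out, so biologics are at 0%. A 28-day gap allows it only for first doses on the 29th or later: at most 0.04% of systemic records. For 2-week-washout topicals and phototherapy the share is 1.3/0.7/0.3% at look-backs of 52/104/260 weeks, or about 10% if all stops lie 14 to 60 days before first dose.

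**Step 4. Size for year-only stops.** Assumptions, since the documents give no distribution: first-dose day *d* = 0 to 364, evenly spread over a year; true stop evenly spread from *W* days (the washout) to *H* days (the look-back) before first dose. The years match when the gap is at most *d*. For *H* of at least 364, with *n* = 365 − *W*:

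share = [*n*(*n* + 1)/2] / [365 × (*H* − *W* + 1)]

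For systemics, *W* = 28 and *H* = 364: *n* = 337; (337 × 338/2) / (365 × 337) = 56,953 / 123,005 = 46.3%. In the same way:

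| Washout | 52 weeks | 104 weeks | 260 weeks | No same-year stop possible if first dose is before |
|---|---|---|---|---|
| 4 weeks (systemics) | 46% | 22% | 9% | 29 January |
| 12 weeks (biologics) | 39% | 17% | 6% | 26 March |
| 24 weeks (biologics) | 27% | 10% | 3% | 18 June |

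Day-by-day enumeration gave the same shares. These are shares of year-only records, not of subjects.

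**Step 5. Where the imputed dates go.** The visible text uses them to sort drugs into the prior and concomitant tables of 2.4.4. The primary imputation model (SAP 5.4.1.2) includes "failure to at least one previous biologic (yes/no), and number of previous systemic therapies as additional covariates", but the SAP names no source for these variables.

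**The case against.** The strongest reply is that placing uncertain dates on the concomitant side is a recognised conservative convention. That holds where it is unknown whether use continued. It does not justify overriding a record taken at screening as already stopped.

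A second reply is that few such records will survive. Protocol 8.1 requires full verification of eligibility, and 8.3 provides for queries on missing values. A bare year equal to the first-dose year leaves the washout unverified and invites a query. This stands as a reason to expect low numbers. It does not repair the rule for what remains.

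Third, a reclassified record need not vanish from the report: the psoriasis-specific summaries in 2.4.4 may combine prior and concomitant use. This also stands; only the general tables by ATC code clearly shift. Those tables count subjects, so the length of the false on-study interval does not enter them. Nor does any visible text describe a prohibited-medication check run on imputed dates.

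**Conclusion.** The point holds in a limited form. A previous therapy with a year-only stop in the year of first dose is moved from prior to concomitant by the plan's own rules. The same-year condition needs no assumption; the percentages rest on even spread of first doses and stops, and fall quickly as the look-back lengthens. The share of partial dates is not given, so the number of subjects cannot be estimated. The matter is minor: descriptive tables would carry false entries of prohibited therapy.

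Three stronger readings are tempting, and the documents do not support them.
- **All year-only history is dated onto the treatment period.** It is not: earlier calendar years stay before first dose. Nor is 46% a general figure; it belongs to 4-week-washout systemics at a one-year look-back.
- **The primary analysis is affected.** No text derives the two imputation covariates from imputed dates. Protocol 6.2.2 collects previous psoriasis treatments and reasons for stopping as psoriasis history, and SAP 2.3.2 lists previous exposure and failure as baseline characteristics. The source may already be the form.
- **Post therapies are misclassified in the same way.** SAP 5.1.3.2 ("Post therapies date imputation") has the same bare pointer and can produce odd dates. But a drug begun after last dose and within the 84-day window is concomitant under 2.4.4 anyway, so its class mostly does not change.

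**What to change.** Replace the cross-reference in SAP 5.1.3.1 with a rule such as:

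> For records on the previous psoriasis therapies or prior medications page that were recorded as stopped (not ongoing) at screening or randomization, the imputed end date is the earlier of the 5.1.3 date and the day before first dose.

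This reduces misclassification of washed-out year-only records to zero by construction. It leaves a therapy recorded as still ongoing under the present rule. As a precaution, state in SAP 5.4.1.2 that previous biologic failure and number of previous systemic therapies are taken from the previous-therapy CRF page.

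The cost is two SAP sentences and a small change to the date derivation. No new data are needed if the page records whether a therapy had stopped. The documents do not show the page layout, so this should be confirmed first.

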5.1.3.1 Prior therapies date imputation

See [Section 5.1.3](#).

5.1.3.2 Post therapies date imputation

See [Section 5.1.3](#).

5.1.3.3 First diagnosis date (Pso, PsA) imputation

1. If the first diagnosis day/ month are missing and the year is non-missing:
 - a. If the year part of the first diagnosis date is equal to the year part of the inform consent date, then the imputed first diagnosis date is set to the year start point (01JanYYYY).
 - b. Otherwise the imputed first diagnosis date is set to the mid-year point (01JulYYYY).
2. If the first diagnosis day is missing and the month/year are non-missing:
 - a. If the month and year part of the first diagnosis date is equal to the month and year part of the inform consent date, then the imputed first diagnosis date is set to the month start point (01MONYYYY).
 - b. Otherwise the imputed first diagnosis date is set to the mid-month point (15MONYYYY).

